7.3.2 Efficacy procedures

7.3.2.1 Incremental recovery of Factor VIII (as of Amd 1)

Samples for FVIII trough levels will be collected in the *clinic* before the next planned *prophylactic infusion* as scheduled. Recoveries should be performed in conjunction with planned prophylaxis *infusions, using the subject's usual dose (exception, during optional PK). Infusions given at study visits will not be recorded in the EPD, but in the site patient records, which will be the source document and will be used to enter this information in the CRF. (as of Amd 1)*

Levels of *BAY 81-8973* will be determined in a central laboratory with the chromogenic *method. (as of Amd 1)*

FVIII trough levels will be determined in the blood samples collected before the *scheduled BAY 81-8973 infusions* at Baseline, Month 1, Month 2, and Month 6 (or final visit) *in Part A; or at Baseline, ED 20, and final visit (ED 50) in Part B.* The measurement should be performed *at least 48 h after last infusion of BAY 81-8973. (as of Amd 1)*

Incremental recovery at 20-30 min after end of *infusions (as of Amd 1)* will be determined at Baseline, Month 1, 2, Month 6 (or final visit), *1st extension visit and final extension visit (as of Amd 6).* Incremental recovery should only be measured when the subject is not actively bleeding. The exact sampling times before and after *infusion (as of Amd 1)* have to be documented in the CRF.

A determination of recovery should also be performed with the confirmatory inhibitor test (as of Amd 7).

7.3.2.2 Treatment logs / bleeding verification

Treatment (as of Amd 1) logs are commonly used for hemophilia subjects for documentation of their home treatment. Home treatment and bleeding frequency are key variables evaluated in this study. Study specific logs will be provided in national language. The preferred system for this study will be EPD devices since they are interactive, allow for real time data transmission, record-stamp date and time of fulfillment and facilitate the clarification of data with the site and also the data cleaning process.

Subjects/parents/caregivers will be provided with EPDs for the whole study. At Screening and Baseline visits, subjects and parents/caregivers will be trained in the use of the device. These logs will be used to collect the *treatment (as of Amd 1)* data and bleeding episodes by the parents/caregivers or subjects, and interact on a *regularly scheduled (as of Amd 1)* basis with the investigator or delegate to verify and complete the *data on (as of Amd 1)* the EPD. Thus, the EPD will be considered the source for these data.

For each *use* of study medication including the *infusions* administered during a planned visit for evaluation of recovery, information must be recorded on the *Treatment (as of Amd 1)*

Logs as follows:

1. Date and time
2. Lot numbers / number of vials administered

3. Reason for *treatment (as of Amd 1)* (prophylaxis, spontaneous bleed first treatment, trauma bleed first treatment, follow-up treatment, surgery, other). ***(If an infusion is given in response to a fall or identified trauma, such as may occur when a child has an uncomplicated blow to the head and there is no clinical sign or evidence of bleeding, the event should be recorded as prophylaxis.) (as of Amd 1)***

If treatment is for a bleeding episode: site of bleeding, severity (severe, moderate, mild), and response to treatment (excellent, good, moderate, *poor, too early to tell*) ***are to be recorded. If 'too early to tell' is entered, the subject will be queried for a response the next time they use the device. For guidance to the subject or their caregivers, the following definitions for response to treatment are suggested. Individual subject responses may vary (as of Amd 1):***

- ***Excellent: Abrupt pain relief and /or improvement in signs of bleeding with no additional infusion administered (as of Amd 1)***
- ***Good: Definite pain relief and/or improvement in signs of bleeding, but possibly requiring more than one infusion for complete resolution (as of Amd 1)***
- ***Moderate: Probable or slight improvement in signs of bleeding, with at least one additional infusion for complete resolution (as of Amd 1)***
- ***Poor: No improvement at all between infusions or condition worsens. (as of Amd 1)***

7.4 Pharmacokinetics (optional – consent required) (as of Amd 1)

Participation in the PK evaluations is optional. The minimal number of subjects in the optional PK is 6. If consent/*assent is obtained, PK will be assessed using the (as of Amd 1)* sampling time points *specified in this protocol (as of Amd 1)*. The pharmacokinetics of the study drug in plasma *can be determined at any time, and should be scheduled to coincide with a scheduled visit to measure incremental recovery, if possible (as of Amd 1)*. There must be a washout of previous FVIII of at least 48 h before the first *infusion (as of Amd 1)* of study drug and the subject must have no signs or symptoms of an acute bleeding episode. ***All samples will be processed in the central laboratory. (as of Amd 1)***

Subjects will be administered a dose of 50 IU/kg. Blood samples will be obtained pre-*infusion (as of Amd 1)* and at 20-30 min, ***4 h, and 24 h (as of Amd 1)*** after the end of *infusion (as of Amd 1)* of study medication. FVIII levels will be determined by the chromogenic assay. Details of the blood sampling and processing procedures for all laboratory measurements will be provided in ***the Laboratory Manual, developed by the central laboratory (as of Amd 3)***, that accompanies this protocol. ***A dose preparation worksheet will be provided in the Pharmacy manual (as of Amd 1).***

Note to investigators: In compliance with EMA guidance and for patient safety, no more than 1% blood volume may be obtained at any one visit, and no more than 3% may be taken in one month (see Section 14.3). If additional PK samples are taken, the total volume of blood drawn in 24 h will be too high for infants weighing less than 9 kg, who must therefore be excluded from the PK sub-study. (as of Amd 3)

Based on the plasma concentration time data the following pharmacokinetic parameters will be calculated: Maximum concentration (C_{max}), recovery, AUC, half-life ($t_{1/2}$), MRT and clearance (CL).

7.5 Safety

7.5.1 Adverse events

7.5.1.1 Definitions

Definition of adverse event (AE)

In a clinical study, an AE is any untoward medical occurrence (i.e., any unfavorable and unintended sign [including abnormal laboratory findings], symptom or disease) in a subject or clinical investigation subject after providing written informed consent for participation in the study. Therefore, an AE may or may not be temporally or causally associated with the use of a medicinal (investigational) product.

A surgical procedure that was planned prior to the start of the study by any physician treating the subject should not be recorded as AE (however, the condition for which the surgery is required may be an AE).

In the following differentiation between medical history and AEs, the term “condition” may include abnormal, eg, physical examination findings, symptoms, diseases, laboratory values.

- Conditions that started before signing of informed consent and for which no symptoms or treatment are present until signing of informed consent are recorded as medical history (eg, seasonal allergy without acute complaints, abnormal laboratory finding at screening).
- Conditions that started before signing of informed consent and for which symptoms or treatment are present after signing of informed consent, at unchanged intensity, are recorded as medical history (eg, allergic pollinosis).
- Conditions that started or deteriorated after signing of informed consent will be documented as AEs.

Note: Any bleeding event occurring during the study will not be documented as *an* AE, because this *event (as of Amd 1)* is captured in the assessment of efficacy. However, if the bleed requires hospitalization, it must be reported as a Serious Adverse Event (SAE) (see Section 7.5.1.4).

Definition of serious adverse event (SAE)

An SAE is classified as any untoward medical occurrence that, at any dose, meets any of the following criteria (a – f):

- a. Results in death
- b. Is life-threatening

The term ‘life-threatening’ in the definition refers to an event in which the subject was at risk of death at the time of the event, it does not refer to an event which hypothetically might have caused death if it were more severe.

- c. Requires in subject hospitalization or prolongation of existing hospitalization

A hospitalization or prolongation of hospitalization will not be regarded as an SAE if at least one of the following exceptions is met:

- The admission results in a hospital stay of less than 12 hours
- The admission is pre-planned
(i.e. elective or scheduled surgery arranged prior to the start of the study)
- The admission is not associated with an AE
(eg, social hospitalization for purposes of respite care).

However, it should be noted that invasive treatment during any hospitalization may fulfill the criterion of ‘medically important’ and as such may be reportable as an SAE dependent on clinical judgment. In addition, where local regulatory authorities specifically require a more stringent definition, the local regulation takes precedence.

- d. Results in persistent or significant disability / incapacity

Disability means a substantial disruption of a person’s ability to conduct normal life’s functions.

- e. Is a congenital anomaly / birth defect
- f. Is another medically important serious event as judged by the investigator.

Note: Any inhibitor development is considered an SAE.

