14.2 Standard of Care

The dosage necessary to achieve hemostasis depends upon the type and severity of the bleeding episode, according to the following general guidelines: (Source: Package Insert Kogenate Bayer). In this protocol, minor surgical procedures are defined as any surgical procedure (elective or emergent) that does not involve general anesthesia and/or respiratory assistance (eg, minor dental extractions, incision and drainage of abscess, or simple excisions). Major surgical procedures are defined as any surgical procedure (elective or emergent) that involves general anesthesia and/or respiratory assistance in which a major body cavity is penetrated and exposed, or a substantial impairment of physical or physiological functions is produced (eg, laparotomy, thoracotomy, craniotomy, fracture).

Degree of hemorrhage/ Type of surgical procedure	Factor VIII level required (%) (IU/dL)	Frequency of doses (hours)/ Duration of therapy (days)
Hemorrhage		
Early hemarthrosis, muscle bleed or oral bleed	20 – 40	Repeat every 12 to 24 hours. At least 1 day, until the bleeding episode as indicated by pain is resolved or healing is achieved.

Degree of hemorrhage/ Type of surgical procedure	Factor VIII level required (%) (IU/dL)	Frequency of doses (hours)/ Duration of therapy (days)
More extensive hemarthrosis, muscle bleed or hematoma	30 – 60	Repeat infusion every 12 – 24 hours for 3 – 4 days or more until pain and disability are resolved.
Life threatening bleeds such as intracranial bleed, throat bleed, severe abdominal bleed	60 – 100	Repeat infusion every 8 to 24 hours until threat is resolved
Surgery		
Minor including tooth extraction	30 – 60	Every 24 hours, at least 1 day, until healing is achieved.
Major	80 – 100 (pre- and postoperative)	a) By bolus injections Repeat infusion every 8 – 24 hours until adequate wound healing occurs, then continue with therapy for at least another 7 days to maintain a factor VIII activity of 30% to 60%

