6.4.1 Adverse events

The investigator has to record on the respective CRF pages all adverse events occurring in the period between the signing of the informed consent form and the end of the follow-up phase. The original terms used by investigators to report AEs via the CRFs will be coded using the Medical Dictionary for Regulatory Activities (MedDRA).

For each AE, the number and percentage of subjects who experienced at least 1 occurrence of the given event will be tabulated according to the affected primary system organ class (SOC) and preferred term (PT) by dose cohort and dose actually received. A total column will be included in all safety summaries.

Frequency tables, showing an overall summary of number of subjects with drug-related AEs, SAEs and AESIs will be given, and will include the following information:

- maximum intensity for any AE,
- AE related deaths,
- AE resulting in permanent discontinuation of study drug,
- treatment emergent AE.

AEs will be considered treatment-emergent if they begin after the first administration of study drug and they do not start after more than 7 days after the last administration. Determination of whether or not an event is treatment-emergent will be derived after the missing or incomplete AE start date is imputed. In case an adverse event starts on the day of first administration of study drug and the time of onset is not known, the event is considered to be not treatment emergent, if it is reported to occur before the first dose of study drug. In all other cases the event is considered to be treatment emergent. Inhibitors will be defined as treatment-emergent if they develop after first study drug application. Imputation rules for missing and incomplete AE start are described in section 4.3.

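### The protocol's note on bleeds names hospitalization as the only trigger for SAE reporting, which conflicts with its own SAE definition and could leave a fatal, life-threatening or disabling bleed without admission unreported

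*Protocol*

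**What the plan says.** Protocol section 7.5.1.1 (Definitions) closes its AE definition with a note on bleeds. The rule is "Any bleeding event occurring during the study will not be documented as" an AE, on the ground that bleeds are already captured under efficacy. One exception follows: "However, if the bleed requires hospitalization, it must be reported as a Serious Adverse Event (SAE) (see Section 7.5.1.4").

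The SAE definition comes directly after: "An SAE is classified as any untoward medical occurrence that, at any dose, meets any of the following criteria", listed a to f. Criterion a is "Results in death" and criterion b is "Is life-threatening". Criterion c is hospitalization, d is persistent or significant disability, e is congenital anomaly, and f is another event the investigator judges medically important. Criterion c has its own exceptions. One reads "The admission results in a hospital stay of less than 12 hours"; another covers an admission not associated with an AE.

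Section 7.5.1.2.1 (Seriousness) asks for the seriousness judgment for each AE. Section 7.5.1.4 requires every SAE to reach the sponsor within 24 hours of the investigator's awareness.

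The Part B SAP (version 2.0, section 6.4.1) builds its safety tables on AEs, SAEs and AEs of special interest, and includes a line for "AE related deaths". The Part A SAP (section 6.4) summarizes treatment-emergent AEs.

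**The concern.** In this disease a serious bleed is both a failure of treatment and a safety event. The protocol expects such bleeds: section 14.2 has a row for "Life threatening bleeds such as intracranial bleed, throat bleed, severe abdominal bleed". Yet for bleeds the note carries over only one of the six seriousness criteria. A site that treats the specific note as overriding the general definition has no instruction to report a bleed that kills, threatens life or leaves lasting disability if the child was not admitted.

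At stake are prompt notice to the sponsor and the completeness of the SAE and death tables in a study whose primary objective includes safety. Efficacy capture does not fill the gap. The diary items in section 7.3.2.2 are site, severity and response to treatment, with nothing for death, threat to life or disability. Under section 6.7 the site reviews diary entries with the family weekly in the main study and monthly in the extension, which is a different timescale from 24 hours.

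**Working it through.** There is no figure to reproduce. The check sets the rules side by side and applies them to the kinds of bleed that can occur.

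**Criteria carried over.** The SAE definition has 6 criteria. The note names 1 of them (c). Criterion e has no bearing on a bleed. That leaves 6 − 1 − 1 = 4 criteria (a, b, d, f) that a bleed could meet and that the note does not mention.

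**Case by case.**

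| Bleed | Note on bleeds | SAE definition | Result |
|---|---|---|---|
| 1. Fatal, life-threatening or disabling, no admission | Not an AE; exception not met | SAE under a, b or d | Ambiguous |
| 2. Otherwise medically important, no admission | Not an AE; exception not met | SAE under f, if so judged | Ambiguous |
| 3. Fatal, life-threatening or disabling, admitted under 12 hours | Report | SAE under a, b or d | Both say report |
| 4. Serious only through an admission under 12 hours | Report | Excepted under c | Direct contradiction |
| 5. Serious only through an admission of 12 hours or more | Report | SAE under c, unless the exception for admissions not associated with an AE is read literally, since a bleed is by rule not an AE | Contradiction on a literal reading |
| 6. Meets no criterion | Diary only | Not an SAE | Consistent |

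**Which text would a site follow in cases 1 and 2?** Three features favour the note.

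- Criterion c already covers hospitalization. If the general definition applied to bleeds unaided, the note's exception would add little. It does most work if bleeds are otherwise outside reporting.
- AEs and SAEs start from the same base, an untoward medical occurrence. The note removes bleeds from the first despite that base, and only the hospitalization sentence expressly brings any back.
- The workflow in sections 7.5.1.2 and 7.5.1.2.1 runs from a recorded AE to a seriousness judgment. A bleed that is never recorded as an AE reaches no stated step at which a, b, d or f would be checked.

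One feature points the other way: section 7.5.1.2.3 uses bleeding at a surgical site as an example when judging AE causality, which does not fit a rule that bleeds are never AEs.

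**Consequence for the tables.** If a case 1 or 2 bleed is neither recorded as an AE nor reported as an SAE, it cannot appear in the AE, SAE or death summaries of either SAP. It may still be counted as a bleed in the efficacy tables, without any mark of seriousness.

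**The case against.** The strongest reply is that the SAE definition already covers these bleeds. Its base is any untoward medical occurrence, not a recorded AE. Bleeds are not carved out, and a, b, d and f need no admission. The note does not say that hospitalization is the only route, so it can be read as waiving routine AE forms and adding one mandatory trigger. This stands: a careful investigator would report a fatal bleed under criterion a. It is why the defect is ambiguity, not exclusion.

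A reader might go further and infer that the plan switches off every criterion except hospitalization, or that all bleeds with stays under 12 hours are exempt. Neither is supported. Nothing disapplies a, b, d or f, and the 12-hour exception qualifies criterion c alone. A life-threatening bleed with a short stay is reportable under b, and the note has no length limit. For bleeds the exception collides with the note; it does not cleanly exempt anything.

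Other safeguards narrow the gap:

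- Section 7.5.1.1 lets invasive treatment during a hospitalization count as medically important, gives way to stricter local rules, and makes any inhibitor an SAE.
- Section 14.5 requires immediate notice to the sponsor when a bleed progresses or fails to improve and an inhibitor is suspected.
- Diary data are transmitted after each entry, and the monthly questionnaire in section 14.3 records hospital, emergency and intensive care visits.

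These help, but none clearly covers a bleed that responded to treatment yet threatened life or left disability without admission.

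**Conclusion.** The point holds as an internal inconsistency with a safety consequence. Sections 7.5.1.1 and 7.5.1.2.1 can be read so that a fatal, life-threatening, disabling or otherwise medically important bleed without admission is not reported within 24 hours and is missing from the safety tables. Separately, the note and the exceptions under criterion c give opposite answers for bleeds serious only through admission.

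The number affected cannot be derived from the documents. I assume zero to a few among the approximately 100 children planned; each could be a death, a threat to life or a lasting disability. The conclusion assumes that some sites would follow the note literally. Site SAE training material, which might say otherwise, is not among the documents.

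A reader might also infer that the data monitoring committee would not see these bleeds. That is unproven: its data sets are set by a charter that is not available, and it reviews efficacy data, where bleeds are counted. Nor does the line for AE-related deaths in the Part B SAP show that bleed deaths are excluded; they would be absent only if never reported.

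**What to change.** Reconcile the note on bleeds, the exceptions under criterion c and section 7.5.1.2.1. The revised text should say that:

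- a bleed meeting any seriousness criterion a to f is recorded and reported as an SAE within 24 hours;
- criteria a, b, d and f apply to bleeds regardless of admission or length of stay;
- the two exceptions under criterion c (stay under 12 hours; admission not associated with an AE) either do or do not apply to bleeds, as the sponsor decides;
- seriousness is judged for bleeds as well as for recorded AEs;
- non-serious bleeds stay in the diary only, as now.

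This changes reporting, not treatment. The cost is a short protocol clarification, a notice to sites and a few extra SAE forms. The SAP tables need no redesign, because a bleed reported as an SAE would enter them in the usual way.

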7.5.1.2 Classifications for adverse event assessment

All AEs will be assessed and documented by the investigator according to the categories detailed below.

7.5.1.2.1 Seriousness

For each AE, the seriousness must be determined according to the criteria given in Section 7.5.1.1.

7.5.1.2.2 Intensity

The intensity of an AE is classified according to the following categories, taking into account the possible range of the intensity of the event:

- Mild
- Moderate
- Severe

7.5.1.2.3 Causal relationship

The assessment of the causal relationship between an AE and the administration of treatment is a clinical decision based on all available information at the time of the completion of the CRF.

The assessment is based on the question whether there was a “reasonable causal relationship” to the study treatment in question.

Possible answers are “yes” or “no”

An assessment of “no” would include:

1. The existence of a clear alternative explanation, eg, mechanical bleeding at surgical site.
- or
2. Non-plausibility, eg, the subject is struck by an automobile when there is no indication that the drug caused disorientation that may have caused the event; cancer developing a few days after the first drug administration.

An assessment of “yes” indicates that there is a reasonable suspicion that the AE is associated with the use of the study treatment.

Factors to be considered in assessing the relationship of the AE to study treatment include:

- The temporal sequence from drug administration: The event should occur after the drug is given. The length of time from drug exposure to event should be evaluated in the clinical context of the event.
- Recovery on drug discontinuation (de-challenge), recurrence on drug re-introduction (re-challenge).
- Subject’s response after de-challenge or subjects response after re-challenge should be considered in the view of the usual clinical course of the event in question.
- Underlying, concomitant, intercurrent diseases:
Each event should be evaluated in the context of the natural history and course of the disease being treated and any other disease the subject may have.
- Concomitant medication or treatment:
The other drugs the subject is taking or the treatment the subject receives should be

examined to determine whether any of them may be suspected to cause the event in question.

- The pharmacology and pharmacokinetics of the study treatment:
The pharmacokinetic properties (absorption, distribution, metabolism and excretion) of the study treatment, coupled with the individual subject's pharmacodynamics should be considered.

